Endpoint 6: The number of the screening tests performed for each individual condition will be compared between the intervention and control PCCs before and after the implementation.

Endpoint 7: Associations between the screening performance of the aggregated infections with different socio-demographic and epidemiological factors, such as, sex, age, geographic areas immunosuppression status, being attended in an intervention centre, fulfilling the screening criteria, among others, will be analysed.

Endpoint 8: Associations between the screening performance of each individual condition with different socio-demographic and epidemiological factors, such as, sex, age, geographic areas immunosuppression status, being attended in an intervention centre, fulfilling the screening criteria, among others, will be analysed.

Exploratory Endpoints

Endpoint 9: The number of migrant patients under follow-up in the hospital after a diagnosis of an infection or FGM will be estimated using the Minimum basic dataset (MBDS).

Endpoint 10: The number of migrant patients under treatment after a diagnosis will be estimated using the data from the EPR systems and MBDS.

Endpoint 11: The prevalence of each condition will be estimated using as the denominator the total number of tested migrant patients for that specific condition.

3. Study Methods

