3.3 Health centres selection, randomisation and masking

Regarding the selection of the participating PCCs in Catalonia, the Fundació d'Investigació en Atenció Primària Jordi Gol i Gurina (DIAP Jordi Gol) research team will find areas where there are referents with an interest in participating in the study. The list of PCCs belonging to these areas, where the referral to the reference laboratory is more feasible, will be provided. With this final list, we will proceed with the randomization stratified by area and by density of migrant population in the area (low, medium and high). For the selection of the PCCs in Andalusia, an IT committee of the Andalusian Health Service (SAS) will provide a list of the possible centres that could participate in the study and the randomization will be carried out using the same stratification method mentioned previously.

The randomization will be performed through a statistical software for each pair of selected health centres stratified by study area. Therefore, for each pair of PCCs, one PCC will be randomly selected to implement the screening programme through the ISMiHealth software, and it will be compared with the other PCC of the same area where the PCCs do follow the current practices in the routine care. In both cases, health professionals will receive a training session on migrant health; the training contents will include for each condition, epidemiological aspects, diagnosis, treatment and the screening recommendation.

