3.4 Study Variables

Data will be collected retrospectively, therefore, the data for all the variables mentioned in Annex 1 will be collected after the year of intervention is completed.

4. Sample size calculation

Considering that all PCCs included in the study have a migration density higher than 7%, we have estimated that by including 32 or more centres in Catalonia we will achieve a difference in difference detection rate of all aggregated infections between intervention and control centres of 2, with a 95% precision. A comparative analysis of the PCCs, in relation to the migration density, will be first performed to select the pairs of centres; then, each pair of selected health centres will be randomized, stratifying by study area, using the Statistical software Stata. To assure the validity of results the intervention centres (where the ISMiHealth tool will support the clinicians' decisions) will be compared to the control centres (where the routine care will be followed) with more similar characteristics.

41 PCCs will participate, 35 in the Catalonian site and six in the Andalusian site. In Catalonia 18 PCCs will be intervention and 17 control, not pairing one of the centres; while in Andalusia there will be 3 intervention and 3 control PCCs. The users of the ISMiHealth tool will be the health professionals of the intervention centres and as participants of the study, they will decide whether to follow the recommendations to screen migrant patients, the indirect beneficiaries of the tool. Approximately 980 health professionals will participate in the study.

5. General Considerations

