intervention level. Linear regressions will be performed for the monthly detection rates of the aggregated infections, and of each individual condition, comparing the intervention and control centres before and during the intervention period.

- Other secondary outcomes will be the proportion of screening tests performed for the aggregated infections and for each individual condition, and factors associated with having a higher screening performance. For this, associations with continuous variables will be evaluated using t-tests, or one-way analysis of variance (one-way ANOVA) for normally distributed quantitative variables, while for not normally distributed quantitative variables, Wilcoxon Rank-Sum and Kruskal-Wallis tests will be carried out. Pearson's chi-square test or Fisher's exact test will be performed to evaluate the associations between categorical variables. In addition, odds ratio (OR) will be estimated (Table 3). Mixed effects logistic regression models will be carried out to identify associations between the screening performance and socio-demographic and epidemiological characteristics, and adjusted odds ratio (aOR) will be estimated, using the region of the PCC as a random intercept (Table 3).
- **b.** The **prevalence** of each individual condition will be estimated and reported with its respective 95%CI. The prevalence for each infection was defined as the number of diagnoses identified by the screening tests performed among the people that were tested. Serology tests will be contemplated for HIV, HBV, HCV, *T.cruzi*, *S.stercoralis* and *Schistosoma spp.* infections; for active TB, chest radiographies will be examined; for FGM, the completed questionnaires and/or referrals to specialists will be considered.

See table 4 for details of the methodology employed for the outcomes.

Data analysis in Andalusia

A similar analysis approach will be carried out in Andalusia but the limited number of PCCs may prevent to estimate the health impact of the tool, therefore, we plan to estimate preliminary effectiveness data. In addition, the analysis for syphilis, latent TB and intestinal parasites will be executed. Nevertheless, because the pilot study will be conducted in six PCCs of one area (Almería), we won't be able to carry mixed-effects logistic regression models and instead, multiple logistic regressions will be performed.

7. Tables and Figures

Table 1. Description of the ISMiHealth sample.

| Variables | Summary statistics | | |

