|---------------------------------|---------------------------------|----------------|----------|-----------------|----------|
| Centre | | | | | |
| Type of centre (urban or rural) | | | | | |
| Index of socioeconomic | | | | | |
| deprivation (MEDEA index) | | | | | |
| Arm of the intervention | | | | | |
| Patient | | | | | |
| Sex | | | | | |
| Age | | | | | |
| Area of birth^ | | | | | |
| Assigned PCT | | | | | |

| Referrals to specialists | | | |
|-----------------------------------|--|---|--|
| Drugs prescribed during the | | | |
| intervention | | | |
| Other diagnoses | | | |
| Immunosuppression status | | | |
| Migrants with screening criteria | | | |
| for XX^ | | | |
| CD4 cell count, viral load and/or | | | |
| laboratory parameters* | | | |
| Hospitalisation | | | |
| Follow-up visits after | | | |
| hospitalisation | | | |
| Mortality | | _ | |

PCT: primary care team, XX: aggregated infections or any of the conditions, OR: odds ratio, aOR: adjusted odds ratio, CI: confidence interval; Region will be used as a random intercept for the logistic regressions; ^Only one of these variables will be added to the multiple logistic regression model due to highly correlation; *When applicable

Table 4. Description of the methodology employed for each outcome

| Outcome | | Methodology |
|--|---------------------------------|------------------------------------|
| Detection rate of all aggre | gated infections | Difference in differences analysis |
| | HIV cases | |
| | Syphilis cases^ | |
| | HBV cases | |
| Detection rate of each | HCV cases | Difference in differences |
| individual condition | active TB cases | analysis |
| | latent TB cases^ | |
| | T.cruzi infection cases | |
| | S.stercoralis infection cases | |
| | Schistosoma spp. infection | |
| | cases | |
| | Intestinal parasites cases^ | |
| | FGM cases | |
| Early diagnoses of | HIV | Bivariate analysis and, if |
| infections | HBV | possible, difference in |
| | HCV | differences analysis |
| Screening tests performed of all aggregated infections | | Bivariate analysis |
| | HIV | |
| | Syphilis^ | |
| | HBV | |
| Screening tests | HCV | |
| performed for each | active TB (chest radiographies) | Bivariate analysis |
| individual condition | latent TB^ (TST/IGRA) | |
| | T.cruzi infections | |
| | S.stercoralis infections | |
| | Schistosoma spp. infections | |

| | Intestinal parasites^ | |
|----------------------------|-----------------------------|--------------------------------|

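### Table 3 tests the arm effect on screening with no allowance for the randomised centre, so its intervals are too narrow wherever uptake differs between centres

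*SAP*

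**What the plan says.** The PCC is the unit of randomisation: SAP 3.3 states that "for each pair of PCCs, one PCC will be randomly selected to implement the screening programme". SAP section 4 forms the pairs on migration density and gives 18 intervention and 17 control PCCs in Catalonia (one unpaired), and 3 against 3 in Andalusia.

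Endpoints 7 and 8 (SAP 2.3) relate screening performance to a list of factors that includes "being attended in an intervention centre, fulfilling the screening criteria, among others, will be analysed". Table 3 accordingly has a row for "Arm of the intervention", with n/N, crude OR, adjusted OR and p-values.

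The methods are in SAP section 6:

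- Crude, Catalonia: Pearson's chi-square or "exact test will be performed to evaluate the associations between categorical variables".
- Adjusted, Catalonia: mixed-effects logistic regression "using the region of the PCC as a random intercept (Table 3". The Table 3 footnote repeats it: "Region will be used as a random intercept for the logistic regressions". Annex 1 lists four Catalan regions. Protocol 7.d likewise names only area.
- Andalusia: because all six PCCs lie in one area, the mixed model is dropped and "instead, multiple logistic regressions will be performed".

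Clustered standard errors are mentioned only for the difference-in-differences model (SAP 6, Catalonia, item a, first bullet; Protocol 7.d). Table 4 does not assign that model to the screening-test outcomes.

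**The concern.** Everyone in a PCC shares its arm, so the arm effect can be no more precise than a comparison of 35 centres (or six). A patient-level test treats patients in one centre as independent given region, and the region intercept removes only differences between four regions. Protocol 7.g itself expects results to differ markedly between PCCs, because uptake depends on the professional and the patient.

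Table 3 is the only adjusted arm comparison of screening in the plan, and readers are likely to take its arm row as the tool's effect on screening. Ordinary differences between centres could then be reported as a significant arm effect. The same fault affects other centre-level rows (urban or rural, deprivation index). Patient-level rows such as sex and age are not the issue.

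**Working it through.** **The plan's own figures.** No ICC, power or design effect is given for Table 3. The only sample-size statement (SAP section 4: 32 or more centres, a difference of 2) concerns the detection rate and gives no SD or power, so there is nothing to reproduce here.

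**Inputs from the documents.** 35 PCCs, 18 v 17, in 17 pairs plus one unpaired; four regions; significance at p<0.05 (taken as two-sided). Patient level is inferred from the n/N column and the patient covariates in Table 3.

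**Assumed, because not given.** Uptake 20%; ICC on the proportion scale; equal numbers m of eligible migrants per PCC; correlation r of PCC effects within pairs; regions of 12/6/9/8 teams (from the order of the Annex 1 list); region SD 0.15 on the logit scale.

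**Formula.** Design effect for the arm contrast: DE = 1 + (m−1) × ICC × (1−r). Actual error of the nominal 5% test: 2 × [1 − Φ(1.96/√DE)]. At ICC 0.01 and m = 200:

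- r = 0: DE = 1 + 199 × 0.01 = 2.99, √DE = 1.73, error 0.257.
- r = 0.5: DE = 1.995, √DE = 1.41, error 0.165.
- r = 0.8: DE = 1.398, √DE = 1.18, error 0.097.

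**Simulation of the stated Catalan model** (region random intercept, Wald test, 4000 null trials per cell, Monte Carlo SE at most 0.8 points):

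| ICC | m | r = 0 | r = 0.5 | r = 0.8 |
|---|---|---|---|---|
| 0.001 | 100 | 5% | 6% | 6% |
| 0.001 | 1000 | 17% | 11% | 8% |
| 0.01 | 100 | 17% | 11% | 7% |
| 0.01 | 200 | 26% | 17% | 10% |
| 0.01 | 500 | 41% | 29% | 18% |
| 0.05 | 1000 | 78% | 70% | 57% |

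At ICC 0 the model holds its 5%. Chi-square is within about 1 point of these figures. A within-pair t-test on PCC results gives 4–6% throughout. PCC-level regression with region fixed gives 4–5% at r = 0 and is conservative (0–5%) when pairs correlate.

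**Dependence on the ICC scale.** A separate simulation with 10% uptake and ICC 0.01 on the latent logistic scale gave 13% at m = 200 and 35% at m = 1000. The two agree: the latent variance is 0.01 × 3.29/0.99 = 0.0332, so the proportion-scale ICC is about 0.1 × 0.9 × 0.0332 = 0.003. The formula then gives DE = 1.6 and error 0.12 at m = 200, and DE = 4.0 and error 0.33 at m = 1000.

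**When it starts to matter.** Error reaches 10% when 1.96/√DE = 1.645, that is, when (m−1) × residual ICC = 0.42: m = 43 at ICC 0.01, 85 at 0.005, 421 at 0.001. For scale, 980 professionals / 41 PCCs is about 24 per PCC, so m = 100 is about 4 migrants each. If the 980 are only those in the 21 intervention PCCs, it is about 47 per PCC and 2 migrants each.

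**Andalusia** (plain logistic, 3 v 3, 20,000 trials), at r = 0 / 0.5 / 0.8: 6 / 6 / 5% (ICC 0.001, m = 100), 25 / 16 / 10% (0.01, 200), 78 / 70 / 55% (0.05, 1000).

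**Assigned team as a covariate.** An intercept, arm and 34 team dummies make 36 columns of rank 35, so arm cannot be estimated beside team fixed effects.

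**The case against.** - **Assigned team is listed in Table 3.** The SAP does not say how it enters. As a random effect it would largely remove the fault. However, the text and the footnote name region as the random intercept and no other. As fixed dummies, team is aliased with arm. The error rates above apply when team is left out of the adjusted model. The crude tests are at fault either way.
- **These are association analyses, and the arm comparison of screening belongs to Endpoints 5–6.** In part this stands. Arm is one row among many, and the list includes variables that follow testing (referral, hospitalisation, mortality), so the adjusted odds ratio is not a clean effect estimate in any case. But arm is a named factor with its own p-value.
- **The size is unknown.** This stands. Catalan results run from 5% to 78% over assumed inputs. The other Table 3 covariates may absorb some between-PCC variation, which places the rates at the upper end for a given total ICC. Inflation is small for conditions with few eligible migrants per PCC.
- **Andalusia is already labelled preliminary** (SAP 5.1). True, so little rests on it. The protocol (4.1.2) also gives seven centres there against the SAP's six; the figures here use six.

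**Conclusion.** The plan is wrong as written for the arm row and other centre-level rows of Table 3. The direction is certain whenever uptake varies between PCCs within region or pair. The size is not: it depends on the ICC left within pairs after adjustment and on eligible migrants per PCC, neither of which is documented. The error is near nominal at ICC 0.001 with 100 migrants per PCC, and about 10–26% at ICC 0.01 with 200, depending on how well the pairs match. The primary difference-in-differences analysis is outside this point.

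For Endpoints 5–6 only a clarification is needed. Table 4 says bivariate analysis without stating the unit: tests on PCC totals would be valid, while patient-level tests would share the fault. This should be fixed before the data are analysed, but it concerns secondary analyses.

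**What to change.** 1. **Catalan adjusted model.** Replace the region intercept with a random intercept for the randomised team, with region as a fixed effect and pair or migrant-density stratum where feasible. Use the 35 teams named under pct_name, not the 40 attended sites under pcc. Do not enter assigned team as a fixed covariate beside arm.
2. **Test of arm.** Use a t reference or, better, a PCC-level test. With a team intercept at pair correlation 0, a normal Wald test still gave 4–9% and t(30) gave 4–7%.
3. **Crude arm comparisons.** Make them at PCC level, paired where possible, or with cluster-adjusted tests.
4. **Endpoints 5–6.** State that the PCC is the unit, and compare before-to-after changes in PCC-level results between arms.
5. **Andalusia.** Analyse the six PCC-level proportions and report estimates with intervals.
6. **Data.** Confirm that the patient's team is in the extract. Protocol 7.d and SAP Table 1 list it, but the patient block of Annex 1 does not; a map from sites to teams would also serve.

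The cost is SAP wording and wider intervals. At ICC 0.01 and m = 200 the arm interval is 1.73 times as wide (1.80 with t(30)). At pair correlation 0.5 with pairs in the analysis it is 1.41 times as wide (1.53 with t(16)). The uptake difference detectable with 80% power is 2.80 × √[(2/17.5) × 0.16 × DE/200]: 2.7 points if clustering is ignored (DE = 1), 4.6 at DE = 2.99 (4.8 with t) and 3.8 at DE = 1.995 (4.0 with t). In Andalusia the 4-df critical value of 2.78 replaces 1.96, which is 42% wider before between-PCC variance is added.

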A pragmatic cluster controlled randomised trial will be conducted in 41 PCCs of Catalonia and Andalusia to explore and assess the effectiveness of the digital tool ISMiHealth. In Catalonia, 35 PCCs will compose the sample size (see sample calculation below) and in Andalusia 7 centres will be selected to conduct the pilot study. See Annex 3 and 4 for the list of the participating centres. Eligible participants will be Health professionals working at the corresponding PCCs. Indirect participants will be migrant populations attended at Primary care (aged \geq 14 years in Andalucía and \geq 15 years in Catalonia), included in the definition of the targeted migrant population (people coming from countries in the geographic areas of Africa, Latin-America, Asia and Eastern Europe following the categorization of the UN Statistical Commission), that are attending the PCCs for any reason. No exclusion criteria will be set concerning the year of arrival to provide the screening recommendations except for active TB where a limit of five years since the arrival to the host country will be established. These criteria will be established since all the infections, except for active tuberculosis, are chronic infections and because a higher risk of such infections has also been seen in long term migrants.

b. Health centres selection, randomisation and masking.

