Regarding the selection of the participating PCCs in Catalonia, the IDIAPJGol research team will find areas where there are referents with an interest in participating in the study. The list of PCCs belonging to these areas, where the referral to the reference laboratory is more feasible, will be provided. With this final list, we will proceed with the randomization stratified by area and by density of migrant population in the area (low, medium and high). For the selection of the PCCs in Andalusia, an IT committee of the Andalusian Health Service (SAS) will provide a list of the possible centres that could participate in the study and the randomization will be carried using the same stratification method mentioned previously. The randomization will be performed through a statistical software for each pair of selected health centres stratified by study area. Therefore, for each pair of PCCs, one PCC will be randomly selected to implement the screening programme through the ISMiHealth software, and it will be compared with the other PCC of the same area where the PCCs do follow the current practices in the routine care. However, one of the seven centres will not be paired, but will participate of the intervention. In both cases, health professionals will receive a training session on migrant health; the training contents will include for each condition, epidemiological aspects, diagnosis, treatment and the screening recommendation.

In addition, a group informed consent will be required to be signed by the Director or a responsible of each PCC where they will agree that their respective PCC will participate in the study.

c. Implementation strategy.

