5.4 Interim Analysis and Data Monitoring

No interim analysis will be conducted. However, the Sistema d'Informació dels Serveis d'Atenció Primària (SISAP) will supervise the technical monitoring of the tool in the implementation phase of the study. Simultaneously, aggregated data will be obtained via SIDIAP during the process of implementation of the tool in the Catalan Institute of Health with the sole objective of technical monitoring to identify alert errors and provide subsequent remediation.

6. Data analysis

Since the ISMiHealth tool is in different phases of implementation in each site, and the algorithms are based on different recommendations, there will be two independent data analyses: i) in Catalonia, the health impact of the tool will be evaluated in 35 PCCs; and ii) in Andalusia, the preliminary effectiveness data will be estimated in the six PCCs where the tool will be pilot tested.

The precision for the reporting of the results will be 95%, considering statistically significant p.values<0.05.

First, for the description of the sample and data obtained from the screening program in each study site, summary statistics will be presented as frequencies for categorical variables, as means with standard deviations (SD) for normally distributed continuous variables and medians with interquartile range (IQR) for non-normally distributed continuous variables (Table 1 and 2).

Data analysis in Catalonia

- a. Health impact of the tool. The effectiveness of the tool will be evaluated and compared between the intervention and control centres. Significant deviations between intervention and control centres before the implementation of the screening program will be suggestive of the main underlying assumption, presenting parallel trends prior to implementation.
 - The primary outcome of the study will be the detection rate of the aggregated infections, while the detection of the individual conditions will be considered as secondary outcomes of the study. To analyse the effect of the intervention on the outcomes, difference in differences approach will be performed using a generalized linear model. Intervention and control PCCs will be compared before and after implementation with respect to the monthly detection rate. Standard errors will be clustered at the

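### Andalusia's six centres inherit the clustered difference in differences and the p<0.05 rule with no small-sample method, so their error rate is unknown and could be too high or too low

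*SAP*

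**What the plan says.** SAP section 6 opens by naming two independent analyses, one per site, and then sets one rule before either is described: "The precision for the reporting of the results will be 95%, considering statistically significant p.values<0.05". Nothing exempts Andalusia.

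For Catalonia, a "difference in differences approach will be performed using a generalized linear model". Standard errors are to be clustered at what the SAP calls the intervention level. The same section also describes linear regressions on the monthly rates. Protocol section 7 calls the errors sandwich-robust. Neither document gives a small-sample correction, a reference distribution or a randomisation test.

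For Andalusia: "A similar analysis approach will be carried out in Andalusia but the limited number of PCCs may prevent to estimate the health impact". SAP Table 4 assigns difference in differences to conditions flagged as Andalusia-only (syphilis, latent TB, intestinal parasites), so the method does reach this site. The one stated change of model is plain multiple logistic regression in place of the mixed-effects version for screening performance. SAP sections 5.1 and 6 limit the site to preliminary effectiveness results.

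On design, SAP section 4 states that "in Andalusia there will be 3 intervention and 3 control PCCs", and section 3.3 that "for each pair of PCCs, one PCC will be randomly selected to implement the screening programme". Protocol section 4 differs: "in Andalusia 7 centres will be selected to conduct the pilot study", and "one of the seven centres will not be paired, but will participate of the intervention".

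**The concern.** Sandwich errors clustered on a unit are justified when there are many such units. With three per arm, the variance estimate is biased downwards and very noisy, and a normal or lightly adjusted reference does not make up for this. The SAP recognises that six centres are few, but its response is to label the output as preliminary. A label alters neither the width of an interval nor the error rate of a test.

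At stake is the reading of the Andalusian results. Table 4 gives this site 12 detection-rate outcomes, each of which would be judged against 0.05 by a procedure whose true error rate the plan does not control.

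**Working it through.** The plan states no error rate, power or sample size for Andalusia, so there is no figure to reproduce.

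**Inputs.** Six centres, 3 v 3 (SAP section 4). One centre drawn per pair (SAP section 3.3). Threshold 0.05 (SAP section 6), taken as two-sided because sidedness is not stated. Twelve outcomes (Table 4): the aggregate, ten infections and FGM.

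**1. Randomisation floor (exact).**
- Paired, as planned: 2^3 = 8 allocations; smallest two-sided p = 2/8 = 0.25.
- Pairing ignored: C(6,3) = 20 allocations; smallest two-sided p = 2/20 = 0.10. One-sided it is 1/20 = 0.05, which still does not satisfy p<0.05.
- Protocol's seventh centre: it goes to intervention without a draw, so the floor stays at 0.25.

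**2. Cluster unit (assumption).** Read literally as the trial arm, the intervention level gives two clusters. In a saturated difference-in-differences model their scores sum to zero, so the robust variance is degenerate. I therefore take the centre as the cluster.

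**3. Size in the balanced linear case, changes uncorrelated within pairs.** Each centre contributes one before-after change. The uncorrected sandwich variance is 2/3 of the unbiased two-sample variance (4 df). With G/(G-1) = 6/5 it is (2/3)(6/5) = 0.80 of it. Size = P(|t4| > critical value x sqrt(ratio)).

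| Reference | Effective cut-off on t4 | True size |
|---|---|---|
| Normal, uncorrected | 1.96 x sqrt(0.667) = 1.600 | 18.5% |
| Normal, G/(G-1) | 1.96 x sqrt(0.80) = 1.753 | 15.4% |
| t on 5 df, G/(G-1) | 2.571 x sqrt(0.80) = 2.299 | 8.3% |

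Simulation of the linear model with six centres agrees: 14.5-19% (normal) and 6-9% (t on 5 df).

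**4. Count model or unequal centres.** Poisson difference in differences, 48 + 12 months assumed, 20,000 runs per setting. Equal centres: 17-24% (normal), 10-12% (t on 5 df). Unequal centres (SD of log size 0.3 to 1.0): 18-35% and 10-21%.

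**5. Positive within-pair correlation.** Balanced linear case with G/(G-1), 1,000,000 draws per row. The correlations are assumed, because the documents give none.

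| Correlation of changes | Normal | t on 5 df | Paired t, 2 df |
|---|---|---|---|
| 0 | 15.4% | 8.3% | 5.0% |
| 0.5 | 7.7% | 3.7% | 5.0% |
| 0.7 | 4.6% | 2.1% | 5.0% |

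**6. Expected false positives over 12 outcomes, no true effect, zero correlation.** 12 x 0.083 = 1.0; 12 x 0.154 = 1.85, about 1.9; at a true 5%, 12 x 0.05 = 0.6. Rare conditions may depart from these approximations.

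**The case against.** The strongest reply is that the plan never commits to the procedure whose error rate is calculated here. Clustering by centre is inferred from a phrase about the intervention level and from the word similar, and the sandwich wording appears only in the protocol. The reference distribution and model family are open. Pairs are chosen to resemble each other and all six centres lie in one area, so positively correlated changes are plausible, and step 5 shows that the test could then be near nominal or conservative. This stands. A reader might infer that the Andalusian test is falsely significant 15-24% of the time; that range needs a normal reference and uncorrelated changes, and the documents specify neither.

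It is also fair that the SAP proposes no randomisation test, so the 0.25 floor does not show that valid inference is impossible. A t-test on the six centre-level changes (4 df) holds 5% when changes are uncorrelated within pairs, and a paired t on three differences can exclude zero. A ban on every p-value at this site would go too far: the screening-performance regressions raise other questions and were not examined.

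Finally, the SAP calls the site a pilot, analyses it separately and admits the shortage of centres. That limits the consequence but supplies no method for six clusters.

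**Conclusion.** The gap is real and should be fixed. The significance rule and a clustered-error difference in differences are carried to six centres with no small-sample method, and no p<0.05 at this site could be backed by the paired randomisation itself.

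The size of the error is conditional. With centre clustering, a balanced linear model and no within-pair correlation, a nominal 5% test has a true size of 8.3% to 15.4% (18.5% uncorrected). Count models and unequal centres push it up; positive within-pair correlation pulls it down, possibly below 5%. The plan therefore cannot show that its test holds 5%, but nor do the documents prove a particular inflation.

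A reader might also infer that a chance finding here would drive roll-out of the tool, or that the trial's main result is compromised. No section ties an Andalusian p-value to a roll-out decision, and the main effectiveness conclusion comes from the separately analysed 35 Catalan centres.

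**What to change.** In the Andalusian part of SAP section 6, for the detection-rate analyses only:

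- Drop the 0.05 rule and state that no significance claim will be made.
- Report each centre's before-after change and the three within-pair differences.
- Take any interval for the aggregate rate from a paired t on the three pair differences (2 df, multiplier 4.30 in place of 1.96). This held 5% at every correlation tried.
- State how the protocol's seventh, unpaired centre is handled, and reconcile six centres in the SAP with seven in the protocol.

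The analysis change takes about two sentences, plus one for the seventh centre, and needs no new data. The price is a visibly wide Andalusian interval, which fits the site's stated pilot purpose. The wording should be settled before the extracted data are analysed.
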